4.3. Exclusion Criteria

Deviations from exclusion criteria are not allowed because they can potentially jeopardize the scientific integrity of the study, regulatory acceptability, or subject safety. Therefore, adherence to the criteria as specified in the protocol is essential.

Subjects meeting any of the following criteria must not be enrolled in the study:

1. Fever with a temperature greater than 100.4°F (38°C) for more than 1 hour or $\geq 101^{\circ}\text{F}$ (38.3°C) in the 24 hours prior to the start of study treatment
2. Women with maternal-fetal conditions that potentially necessitate the need for delivery, such as pre-eclampsia or fetal compromise
3. A fetus with any diagnosis, condition, treatment, or other factor that in the opinion of the investigator has the potential to affect or confound assessments of efficacy or safety (e.g., nonreassuring fetal status, intrauterine growth restriction, major congenital anomaly)
4. Preterm premature rupture of membranes
5. Women with any confirmed or suspected contraindication to prolongation of pregnancy, such as placental abruption, chorioamnionitis, or placenta previa
6. Evidence of polyhydramnios (amniotic fluid index [AFI] >25 cm) or oligohydramnios (AFI <5 cm)
7. Women with co-morbid medical or obstetric conditions that in the opinion of the investigator have the potential to complicate the pregnancy course and outcomes, such as uncontrolled hypertension, uncontrolled diabetes (if known, history of glycosylated hemoglobin $>8\%$ at any time during pregnancy), known or suspected maternal Zika infection during gestation (see SPM for details), or compromise the safety of the subject, such as underlying cardiovascular disorder (specifically ischemic cardiac disease, congenital heart disease, pulmonary hypertension, valvular heart disease, arrhythmias, and cardiomyopathy)
8. Women with a history of substance abuse during the pregnancy or dependency that may have the potential to complicate the pregnancy outcome.
9. Women with any diagnosis, condition, treatment, or other factor that in the opinion of the investigator has the potential to affect or confound assessments of efficacy or safety

10. Women with documented active hepatitis B or hepatitis C viral infection, unstable liver disease (as defined by the presence of ascites, encephalopathy, coagulopathy, hypoalbuminemia, esophageal or gastric varices, or persistent jaundice), cirrhosis, known biliary abnormalities (with the exception of Gilbert's syndrome or asymptomatic gallstones)
11. History of sensitivity to the IPs or components thereof or a history of drug or other allergy that, in the opinion of the investigator or GSK/PPD medical monitor, contraindicates their participation.

4.4. Withdrawal From Study and Discontinuation of IP

The section describes and distinguishes the following:

- Withdrawal of the subject from the study after randomization but before administration of IP (Section 4.4.1.1) and after administration of IP (Section 4.4.1.2)
- Discontinuation of the IP (Section 4.4.2), wherein subjects who receive but then discontinue from IP will not be considered withdrawn from the study and should remain in the study and continue to be followed for efficacy and safety.

4.4.1. Withdrawal From Study

4.4.1.1. Withdrawal From Study Participation After Randomization but Prior to Investigational Product Administration

Any subject with a nonreassuring fetal heart rate pattern, a re-assessment that determines tocolytic therapy is no longer indicated (according to investigator's medical discretion), abnormal levels of alanine aminotransferase (ALT) or bilirubin (if results are available), or a clinically significant abnormal finding on an ECG cannot be dosed and should be withdrawn from the study. The reasons for not dosing a subject will be recorded in the eCRF and source documents. Subjects who are withdrawn prior to receiving randomized IP will not be followed.

A nonreassuring fetal heart rate is defined as either unresolved Category 3 tracings (including either [1] the absence of baseline fetal heart rate variability and any of the following: recurrent late decelerations, recurrent variable decelerations, or bradycardia; or [2] sinusoidal pattern) or at the investigator's discretion.

Dosing may be started before local liver function test results are available; however, if local laboratory results are available before the start of dosing and ALT is $>2 \times$ the upper limit of normal (ULN) or bilirubin is $>1.5 \times$ ULN ($>35\%$ direct bilirubin), the subject should not be dosed and should be withdrawn from the study. An isolated bilirubin $>1.5 \times$ ULN is acceptable if bilirubin is fractionated and direct bilirubin is $<35\%$. See Section 6.3.1 for liver stopping criteria for management of abnormal test results that become available after the start of dosing.

4.4.1.2. Withdrawal From Study Participation After Beginning Randomized Treatment

All subjects who are randomly assigned to and begin treatment (i.e., randomized treatment) should be encouraged to complete all phases of the study, including those who discontinue randomized treatment. However, a subject may voluntarily withdraw from study participation at any time or be withdrawn at any time at the discretion of the investigator for any maternal obstetrical or medical complications after consultation with the GSK/PPD medical monitor. If a subject withdraws from the study, no additional visits can occur or procedures performed, and the subject may request destruction of any samples taken; the investigator must document this request in the site study records.

Subjects who are withdrawn from study participation after starting randomized treatment will not be replaced. Reasons for study withdrawal will be recorded in the eCRF and the subject's source document. A subject may be withdrawn from the study for the following reasons:

- Loss to follow-up
- Subject voluntarily withdrew consent
- Investigator decision to withdraw the subject from participation; investigators must consult the GSK/PPD medical monitor before withdrawing a subject from participation in the study
- Termination of the study by GSK

Subjects who are withdrawn after starting the Inpatient Randomized Treatment Phase and before the Post-Infusion Assessment Phase will be asked to return and complete the assessments specified for the face-to-face post-infusion assessment visit before withdrawing from the study (see Section 3.1.3 and [Table 5](#)). If the subject withdraws after the face-to-face post-infusion assessment visit, the investigator will attempt to contact the subject by telephone to determine if she has delivered and to gather the information specified in Section 3.1.4.

Withdrawal from this study after beginning randomized treatment does not preclude involvement in the separate infant follow-up study.

Should a subject fail to attend the clinic for a required study visit, the site should attempt to contact the subject and reschedule the missed visit as soon as possible. The site should also counsel the subject on the importance of maintaining the assigned visit schedule and ascertain whether or not the subject wishes to and/or should continue in the study based on previous noncompliance.

In cases where the subject is deemed "Lost to Follow-up" (e.g., subject does not return for the rescheduled visit or cannot be reached to reschedule the missed visit), the investigator or designee should make every effort to regain contact with the subject (where possible, 3 telephone calls and if necessary a certified letter to the subject's last known mailing address or local equivalent methods). These contact attempts should be documented in the subject's medical record. Should the subject continue to be unreachable, then and only then will he/she be considered to have withdrawn from the

study with a primary reason of “Lost to Follow-up.” For all other subjects withdrawing from the study, an alternative reason for discontinuation should be recorded in the eCRF.

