Prior to randomization, each subject will be stratified by progesterone treatment and GA determined by (1) known fertilization date, either *in vitro* fertilization or intrauterine insemination or (2) a best estimated due date confirmed or established by the earliest ultrasound performed prior to 24^{0/7} weeks' gestation. The progesterone strata will consist of subjects on established progesterone therapy or subjects not on established progesterone therapy at Screening. The GA strata are 24^{0/7} to 25^{6/7}, 26^{0/7} to 27^{6/7}, 28^{0/7} to 30^{6/7}, or 31^{0/7} to 33^{6/7}.

The Screening Phase will occur on Day 0 and assessments will primarily focus on maternal and fetal safety evaluations prior to dosing. Subjects will be randomly assigned to treatment on Day 1 of the Inpatient Randomized Treatment Phase. The treatment phase will be 48 hours. Subjects who do not experience labor progression and remain undelivered after 48 hours will be managed per the investigator's judgment.

Treatment can be discontinued due to labor progression with imminent delivery, intolerance to treatment, and any contraindication to continuation of randomized treatment. Subjects who discontinue randomized treatment will be asked to remain in the study through the maternal post-delivery assessment and review of the newborn records. Withdrawal from the study should only occur if a subject either refuses to continue or is lost to follow-up.

Subjects who remain undelivered after 48 hours will be scheduled for a face-to-face post-infusion assessment visit for obstetric assessments 1 week (acceptable range: 3 to 14 days) following the Inpatient Randomized Treatment Phase (Note: study documents may reference this visit as the 1-week face-to-face post-infusion assessment visit). The subject will then be contacted every week via telephone to determine if birth has occurred. If the subject delivers the baby prior to the face-to-face post-infusion assessment visit, central laboratory assessments for hematology, chemistry, and liver function tests (see [Table 5](#)) and the assessments for the Delivery Phase (see Section [3.1.4](#)) will be performed.

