4.4.2. Discontinuation of Investigational Product

Subjects who receive but who discontinue from IP will not be considered withdrawn from the study and should remain in the study and continue to be followed for efficacy and safety. Once delivered, newborns will also continue to be followed for safety and outcomes through the 28 days post EDD.

A subject may voluntarily discontinue from the IP at any time. The investigator may also, at his or her discretion, discontinue the IP at any time for any medical reason or maternal or fetal complications. Subjects who discontinue randomized treatment will be managed by the investigator according to standard care.

Subjects who discontinue the IP will not be replaced. Reasons for discontinuation from IP will be recorded in the eCRF and the subject’s source documents.

A subject will also be discontinued from IP under the following circumstances:

1. Labor progression or delivery (vaginal or caesarean section) occurs during the Inpatient Randomized Treatment Phase
2. Intolerance of assigned treatment
3. An obstetric indication for delivery (e.g., nonreassuring fetal status)
4. Contraindication for continuing randomized treatment including, but not limited to, infection (i.e., chorioamnionitis) or placental insufficiency as evidenced by, for example, abruptio placentae, intrauterine growth restriction, nonreassuring fetal status or death, severe pre-eclampsia/eclampsia, maternal bleeding with hemodynamic instability, or other conditions at the discretion of the investigator
5. An abnormal corrected QT interval using Fridericia formula (QTcF) detected during standard care of the subject based on the following criteria:
 - QTcF >500 msec or uncorrected QT >600 msec
 - Change from baseline QTcF value of >60 msec

For subjects with underlying bundle-branch block, treatment should be discontinued in the following circumstances:

- QTcF >500 msec in a subject with a baseline QTcF value of <450 msec
 - QTcF \geq 530 msec in a subject with a baseline QTcF value between 450 and 480 msec
6. Abnormal liver function test result detected during standard care of the subject based on the criteria detailed in Section 6.3.1.

Subjects discontinuing the IP for any of the above reasons can and should continue to receive antenatal steroids (either betamethasone or dexamethasone) for fetal lung maturity if not yet completed and still clinically indicated.

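### Protocol Section 4.4.1.2 allows a complication to end study follow-up of a dosed woman, against the Protocol Summary and Section 4.4.2, and states no delivery or newborn retrieval for early withdrawals

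*Protocol*

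**What the plan says.** Three places in the current protocol govern whether a dosed woman can leave the study.

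- **Protocol Summary, Study Design:** "Withdrawal from the study should only occur if a subject either refuses to continue or is lost to follow-up".
- **Section 4.4.2**, which covers stopping investigational product (IP), including for infection, abruption, severe pre-eclampsia and bleeding: "Subjects who receive but who discontinue from IP will not be considered withdrawn from the study and should remain in the study". Newborns are followed through 28 days after the estimated date of delivery (EDD).
- **Section 4.4.1.2**, which covers withdrawal from the study itself: a woman may "be withdrawn at any time at the discretion of the investigator for any maternal obstetrical or medical complications", once the medical monitor has been consulted. The investigator's decision is also a listed reason, again subject to consulting the monitor.

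Section 4.4.1.2 then sets out what follows: "If a subject withdraws from the study, no additional visits can occur or procedures performed". A woman who leaves between the start of treatment and the post-infusion phase "will be asked to return and complete the assessments specified for the face-to-face post-infusion assessment visit before withdrawing from the study". For a woman who leaves later than that visit, "the investigator will attempt to contact the subject by telephone to determine if she has delivered"; the same call is meant to obtain the delivery and newborn information listed in Section 3.1.4. The separate infant study stays open to her, subject to its own consent.

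For women who withdraw, SAP Sections 11.7.1 and 11.7.3 replace a missing delivery date with the last contact or last record, at which the woman was still undelivered. Sections 11.7.2 and 11.7.4 use a gestational age (GA) at birth completed in the same way as a predictor in the multiple imputation of the neonatal composite and of length of stay.

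**The concern.** Section 4.4.2 already lets the investigator stop IP for a maternal or fetal complication while follow-up continues. The complications clause in Section 4.4.1.2 therefore adds nothing to the power to stop IP. What it adds is the power to end follow-up, and for a class of events that includes maternal adverse events of special interest such as chorioamnionitis and abruption.

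A woman with a complication is one whose delivery time and newborn course are likely to differ from the rest. If she leaves because of it, missingness depends on outcome. It also depends on treatment if complications differ by arm, and blinding does not prevent that. What is at stake is the primary endpoint, the key secondary endpoints built on GA at birth or on newborn records, and the later part of the maternal and newborn safety record.

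**Working it through.** **1. What is retrieved, by time of withdrawal**

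- *IP stopped, woman stays in the study (4.4.2):* delivery data and newborn follow-up through 28 days post EDD.
- *Withdrawn before the face-to-face visit (4.4.1.2):* the face-to-face assessments are requested. No delivery or newborn retrieval is stated.
- *Withdrawn after that visit (4.4.1.2):* a telephone attempt to obtain the Section 3.1.4 information. Nothing is stated for the newborn review through 28 days post EDD (Section 3.1.6).
- *Adverse events:* Section 6.3.10 follows serious events and events of special interest to resolution, stabilization, explanation or loss to follow-up; withdrawal is not a listed end. Section 6.3.8 does not oblige investigators to look for events in former subjects. For a withdrawn woman these two sections pull apart.
- *SAP 11.7.1:* the national-database search for a birth date is stated only for women lost to follow-up.

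**2. What the SAP then does with an early withdrawal**

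The latest GA at entry is 33 6/7 weeks, or 33 × 7 + 6 = 237 days. Treatment lasts 2 days and the face-to-face visit falls at most 14 days later: 237 + 2 + 14 = 253 days = 36 1/7 weeks. The preterm cut-off is 37 × 7 = 259 days. So any woman whose last record is at or before an in-window face-to-face visit is counted as a preterm birth, whenever she actually delivered.

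SAP Section 7.1.2 also pre-assigns deliveries within 1 week of randomization to the imminent-delivery component of the mixture model. A woman last seen within that week would enter it by imputation alone.

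**3. Size, as scale only**

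*The plan's own allowance.* Section 8.2.1 randomizes 330 to obtain 300 with birth data at 10% missing: 300 × 1.10 = 330, which reproduces the stated figure (330 × 0.90 = 297). The allowance is 330 × 0.10 = 33 women, or 16.5 per arm. It covers missing data from all causes and is no estimate of complication-driven withdrawal.

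*Time to delivery.* If a fraction k of an arm has last contact d days before true delivery, the arm's simple mean falls by k × d. Both are assumptions:

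- k = 2%: d = 7, 21, 42 gives 0.14, 0.42, 0.84 days
- k = 5%: 0.35, 1.05, 2.1 days
- k = 10%: 0.7, 2.1, 4.2 days

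The design difference is 9.5 days. With equal k × d in both arms the shift cancels in the difference of simple means; what biases the comparison is the imbalance. The primary estimate comes from a mixture model, so these figures are approximate. At the enrolled size of 97 (about 48 per arm), two women in one arm imputed 28 days early give 2 × 28 / 48 = 1.2 days.

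*Later safety events.* Table 1 of the protocol gives 4% to 6% for primary postpartum hemorrhage: 165 × 0.04 = 6.6 and 165 × 0.06 = 9.9 events per arm at the planned size. Suppose true rates of 6% on retosiban and 4% on atosiban (ratio 1.5), and suppose a fraction w of the affected retosiban women had already been withdrawn for something else, with the hemorrhage never captured. The ratio seen is 0.06 × (1 − w) / 0.04: 1.125 at w = 25% and 0.75 at w = 50%. Loss in one arm only, at these fractions, is an extreme case chosen to show direction.

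**The case against.** Much can be said for the section. It opens by asking that all dosed women be encouraged to complete every phase, and it requires the medical monitor to be consulted before an investigator withdraws anyone. That is a real brake, although no criterion limits the decision.

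Four stronger readings are tempting, and the documents do not support them.

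- *Each such withdrawal removes a mother-infant pair and lowers an arm's incidence of special-interest events by one woman in about 48.* The complication that prompts withdrawal has already happened and is reportable, and maternal adverse events are marked in the withdrawal column of Table 5. The woman stays in the Maternal Safety and ITT populations and her newborn in the neonatal ones. For the triggering event neither numerator nor denominator need change.
- *Section 4.4.1.2 contradicts itself by barring visits and then asking for one.* The assessments are requested before she withdraws and the bar applies afterwards. A telephone attempt is arguably neither a visit nor a procedure.
- *The withdrawal column of Table 5 omits assessments that the section requires.* The section sends early withdrawals to the face-to-face assessments, which have their own column with vital signs, central laboratory tests and fetal heart rate.
- *Withdrawal always ends follow-up of the infant.* A successful telephone contact for a late withdrawal is meant to yield the Section 3.1.4 newborn information, and the infant study remains available.

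The rule in Section 6.3.10 also counts in the plan's favor. However, it covers adverse events. It does not supply the delivery date, length of stay or the composite review, and Section 6.3.8 weakens it for women who have left. The conflict over grounds for withdrawal and the missing retrieval for early withdrawals remain unanswered.

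**Conclusion.** The concern holds as a conflict between sections together with a retrieval gap, and it should be corrected. Loss of follow-up after a complication is possible under Section 4.4.1.2; it is not automatic. What can be lost is delivery time, adverse events after withdrawal and newborn outcomes through 28 days post EDD. The SAP then analyses last contact as delivery and carries that date into the preterm-birth proportions and, through GA at birth, into the imputation of the composite and length of stay.

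The size is unknown, because the documents give no rate of complication-driven withdrawal. The 0.14 to 4.2 days rests on assumed values of k and d and on the loss falling in one arm. The statement that an early withdrawal is counted as preterm rests only on the entry limit, the visit window and the SAP rule, provided no later record exists.

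**What to change.** Reconcile the Protocol Summary, Sections 4.4.1.2 and 4.4.2, and Section 6.3.10 (with 6.3.8) so that a complication alone does not end study follow-up of a dosed woman or her newborn. Leave decisions about IP and clinical care as they are, together with voluntary withdrawal and uses of investigator decision unrelated to complications.

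Separate withdrawal from visits and contact from withdrawal of consent to record review. For any withdrawal where consent to record review has not been withdrawn, including withdrawal before the face-to-face visit, collect the delivery date and the maternal and newborn data by record review, under the release requested at consent (Section 4.2, inclusion criterion 1).

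The cost is protocol wording and record-review effort, with no added visit. The release is requested at consent, so its presence needs checking case by case. Enrollment stopped at 97, so the practical step for this trial is to check the planned listing of reasons for study withdrawal (SAP Listing 2) for investigator-decided cases and retrieve delivery and newborn records where consent permits.

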4.4.2. Discontinuation of Investigational Product

Subjects who receive but who discontinue from IP will not be considered withdrawn from the study and should remain in the study and continue to be followed for efficacy and safety. Once delivered, newborns will also continue to be followed for safety and outcomes through the 28 days post EDD.

A subject may voluntarily discontinue from the IP at any time. The investigator may also, at his or her discretion, discontinue the IP at any time for any medical reason or maternal or fetal complications. Subjects who discontinue randomized treatment will be managed by the investigator according to standard care.

Subjects who discontinue the IP will not be replaced. Reasons for discontinuation from IP will be recorded in the eCRF and the subject’s source documents.

A subject will also be discontinued from IP under the following circumstances:

1. Labor progression or delivery (vaginal or caesarean section) occurs during the Inpatient Randomized Treatment Phase
2. Intolerance of assigned treatment
3. An obstetric indication for delivery (e.g., nonreassuring fetal status)
4. Contraindication for continuing randomized treatment including, but not limited to, infection (i.e., chorioamnionitis) or placental insufficiency as evidenced by, for example, abruptio placentae, intrauterine growth restriction, nonreassuring fetal status or death, severe pre-eclampsia/eclampsia, maternal bleeding with hemodynamic instability, or other conditions at the discretion of the investigator
5. An abnormal corrected QT interval using Fridericia formula (QTcF) detected during standard care of the subject based on the following criteria:
 - QTcF >500 msec or uncorrected QT >600 msec
 - Change from baseline QTcF value of >60 msec

For subjects with underlying bundle-branch block, treatment should be discontinued in the following circumstances:

- QTcF >500 msec in a subject with a baseline QTcF value of <450 msec
 - QTcF \geq 530 msec in a subject with a baseline QTcF value between 450 and 480 msec
6. Abnormal liver function test result detected during standard care of the subject based on the criteria detailed in Section 6.3.1.

Subjects discontinuing the IP for any of the above reasons can and should continue to receive antenatal steroids (either betamethasone or dexamethasone) for fetal lung maturity if not yet completed and still clinically indicated.

Subjects discontinuing the IP who have not yet delivered will continue in the study through delivery and the maternal post-delivery assessment. These subjects will be included in the Intent-to-Treat (ITT) and Safety Populations. Additionally, all infants should be consented for the separate infant follow-up study.

